4.5 Performance and Safety

4.5.1 Subject Characteristics

Date of birth	DD/MMM/YYYY
Gender	Male/Female

Title: CIP with integrated central Amendments 1 and 2 ExufiberAg+01
Page 29(50)

Investigation Code	ExufiberAg+01Final Version	Approval date	2017-05-10
		Amendment 1 Approval date	2017-05-26
		Amendment 2 Approval date	2018-08-07
		Amendment 3 Approval date	2018-08-21
		Amendment 4 Approval date	2019-02-19

Vital signs	Height (cm/feet and inches) Weight (kg/pounds) BMI
Relevant Medical History Relevant such as diabetes, arterial disease lower leg, anemia, cardio-vascular disease, thrombosis, that may affect the evaluation of dressings performance	Medical condition Date of initial diagnosis Past/current Ongoing medication
Relevant Surgical History Relevant such as varicose vein, amputation defined as surgery that may affect the evaluation of dressings performance.	Surgical procedure Date of surgical procedure Past/current Ongoing medication
Type of wound and location of the wound	Venous leg ulcer Arterial leg ulcer Mixed etiology Pressure ulcers (partial) Diabetic foot ulcer Traumatic wounds Partial thickness burns (second degree) Donor site Malignant wounds
Duration of wound	< 1 week ≥ 1 week to <6 weeks ≥ 6 weeks to <12 month ≥12 month

Title: CIP with integrated central Amendments 1 and 2 ExufiberAg+01
Page 30(50)

Investigation Code	ExufiberAg+01Final Version	Approval date	2017-05-10
		Amendment 1 Approval date	2017-05-26
		Amendment 2 Approval date	2018-08-07
		Amendment 3 Approval date	2018-08-21
		Amendment 4 Approval date	2019-02-19

Current wound treatment	Primary dressing (Y/N) Name of the current primary dressing Frequency of dressing change/per week Secondary dressing (Y/N) Name of the current secondary dressing
-------------------------	---

4.5.2 Performance Measurements and Variables

Primary objective	Primary outcome variable
To evaluate changes in exudate status (see Table 1) from baseline to last visit. Dry and healed wounds counts as successful wound	Dry Moist Wet Saturated Leaking

Secondary objective	Secondary outcome variable
To evaluate the status of the wound and peri-wound skin from baseline to last visit (by visit)	Status of the wound and peri-wound skin evaluated by study personnel Exudate nature (Serous/Serosanguinous/Sanguinous/Purulent/NA) Malodour (None, Slight, Moderate, Strong) Redness/Irritation under the Primary dressing (Y/N) Redness/irritation outside the Primary dressing (Y/N) Maceration under the Primary dressing (Y/N) Maceration outside the Primary dressing (Y/N) Wound size (as described in section 4.5.5) Tissue type of the wound bed: Necrotic%, Sloughy%, Granulation% Epithelization%, Other if applicable in % Wound status (Stagnated, Aggravated, Same as baseline, Improved, Healed)

Title: CIP with integrated central Amendments 1 and 2 ExufiberAg+01
Page 31(50)

Investigation Code	ExufiberAg+01Final Version	Approval date	2017-05-10
		Amendment 1 Approval date	2017-05-26
		Amendment 2 Approval date	2018-08-07
		Amendment 3 Approval date	2018-08-21
		Amendment 4 Approval date	2019-02-19

Secondary objective	Secondary outcome variable
To evaluate the handling and technical performance of the dressing from baseline to last visit (by visit)	
Investigator and Nurse Evaluation
 
Primary dressing, ease of application (Very Poor/Poor/Good/Very Good/NA)
 
Primary dressing, ease of removal without moistening the dressing (Very Poor/Poor/Good/Very Good/NA)
 
Primary dressing, can be removed in one piece (Very Poor/ Poor/ Good/ Very Good/ NA)
 
Primary dressing, adherent to the wound bed (Y/N). If Yes, specify:
 
Primary dressing, ability to rehydrate (Very Poor/ Poor/ Good/Very Good/NA)
 
Primary dressing, ease of removal after moistening the dressing (Very Poor/ Poor/ Good/Very Good/NA)
 
Primary dressing, residuals of the dressing material in the wound or surrounding skin (Very Poor/Poor/ Good/ Very Good/NA)
 
Primary dressing, ability to absorb exudate (Very Poor/Poor/Good/Very Good/NA)
 
Primary dressing, ability to absorb blood (Very Poor/Poor/Good/Very Good/NA)
 
Primary dressing, ability to retain exudate (Very Poor/Poor/Good/Very Good/NA)
 
Primary dressing, ability to retain slough (Very Poor/Poor/Good/Very Good/NA)
 
Primary dressing, ability to clean the wound bed (remove blood, pus, slough etc.) (Very Poor/Poor/Good/Very Good/NA)
 
Primary dressing, ability to retain the soft and gelling properties (Very Poor/Poor/Good/Very Good/NA)
 
Primary dressing, ability to retain a balanced moist environment in the wound (Very Poor/Poor/Good/Very Good/NA)

Title: CIP with integrated central Amendments 1 and 2 ExufiberAg+01
Page 32(50)

Investigation Code	ExufiberAg+01Final Version	Approval date	2017-05-10
		Amendment 1 Approval date	2017-05-26
		Amendment 2 Approval date	2018-08-07
		Amendment 3 Approval date	2018-08-21
		Amendment 4 Approval date	2019-02-19

Secondary objective	Secondary outcome variable
	
Primary dressing conforms to the wound contours (Very Poor/Poor/Good/Very Good/NA)
 
Primary dressing, overall experience (Very Poor/ Poor/ Good/Very Good/NA)

To evaluate the dressing stay on ability and preparation of the skin from baseline to last visit (by visit)	
Compression therapy (Y/N/NA)
 
Cleansing (Y/N/NA)
 
Debridement (Y/N/NA)
 
Frequency of dressing change?
 
If Primary dressing is change due to leaking Y/N if yes, please specify
 
 - Dressing, is full - Dressing shrinks and doesn't fill up the wound - Other
To evaluate comfort, conformability and acceptability of the dressing from visit 3 to last visit (by visit) from a subject view	
Subject Evaluation
 
Comfort when wearing the primary dressing (Very Poor/Poor/Good/Very Good/NA)
 
Ease of mobility while wearing the primary dressing (Very Poor/Poor/Good/Very Good/NA)
 
Primary dressing remained in place (Very Poor/Poor/Good/Very Good/NA)
 
Stinging or burning while wearing the primary dressing (Y/N/NA)
 
Primary dressing, overall experience (Very Poor/Poor/Good/Very Good/NA)

Title: CIP with integrated central Amendments 1 and 2 ExufiberAg+01
Page 33(50)

Investigation Code	ExufiberAg+01Final Version	Approval date	2017-05-10
		Amendment 1 Approval date	2017-05-26
		Amendment 2 Approval date	2018-08-07
		Amendment 3 Approval date	2018-08-21
		Amendment 4 Approval date	2019-02-19

Secondary objective	Secondary outcome variable
To evaluate the bioburden from baseline to visit 3	
Microbial detection
 
Change in the aerobic counts (Log CFU/cm²) and microbial diversity from baseline to visit 1b (4 days after baseline)
 
Change in the aerobic counts (Log CFU/cm²) and microbial diversity from baseline to visit 2 (7 days after baseline)
 
Change in the aerobic counts (Log CFU/cm²) and microbial diversity from baseline to visit 3 (14 days after baseline)

4.5.3 Safety Measurements and Variables

To evaluate safety from baseline to last visit	
Signs of clinical infection (Figure 3)
 
Acute wounds
 
Classical signs (new and increasing pain, erythema, local warmth, swelling, purulent discharge) (Y/N)
 
Pyrexia (Y/N)
 
Delayed or stalled healing (Y/N)
 
Abscess (Y/N)
 
Malodour (Y/N)
 
Chronic wounds
 
New, increased or altered pain (Y/N)
 
Delayed (or stalled) healing (Y/N)
 
Periwound oedema (Y/N)
 
Bleeding or friable (easily damaged) granulation tissue (Y/N)
 
Distinctive malodour or change in odour (Y/N)
 
Wound bed discolouration (Y/N)
 
Increased, altered or purulent exudate (Y/N)
 
Induration (hardening of a tissue, particularly the skin, caused by inflammation) (Y/N)

--	--

Title: CIP with integrated central Amendments 1 and 2 ExufiberAg+01

Page 34(50)

Investigation Code	ExufiberAg+01Final Version	Approval date	2017-05-10
		Amendment 1 Approval date	2017-05-26
		Amendment 2 Approval date	2018-08-07
		Amendment 3 Approval date	2018-08-21
		Amendment 4 Approval date	2019-02-19

	
Pocketing-granulation tissue does not grow in a uniform manner across the entire wound, pockets can harbour bacteria (Y/N)
 
Bridging-presence of strands of tissue across the wound bed (Y/N)
 
Adverse Event (AE)/Adverse Device Effect (ADE), Serious Adverse Event (SAE)/Serious Adverse Device Effect (SADE), Device deficiency (DD)

--	--

Title: CIP with integrated central Amendments 1 and 2 ExufiberAg+01
Page 35(50)

Investigation Code	ExufiberAg+01Final Version	Approval date	2017-05-10
		Amendment 1 Approval date	2017-05-26
		Amendment 2 Approval date	2018-08-07
		Amendment 3 Approval date	2018-08-21
		Amendment 4 Approval date	2019-02-19

4.5.4 Identification and quantification of microorganisms presents in the wound

[figure not shown]
This section is only applicable for site no 01 (only subjects enrolled before September 2018) since they are the only site collecting tissue and exudate.

Evaluation of antimicrobial activity of Exufiber Ag+ and Exufiber on wound bioburden by collection of tissue and exudate (specified in Appendix F). Following analysis will be performed on approximately 30 subjects, equally distributed between Exufiber Ag+ and Exufiber.

- ✓ overall quantification of microbial counts by traditional culturing under aerobic conditions
- ✓ identification of bacteria/fungi by Next Generation Sequencing (16S rRNA for bacteria, ITS1 or ITS2 for fungi)
- ✓ evaluate inflammatory biomarkers and virulence factors via collecting wound exudate

4.5.5 Wound size measurement

Figure 2 Measure wound size

Wound size will be measured according to schedule of assessment (4.2.1), if debridement, wound size will be measured before and after debridement, record in inches/mm.

4.5.6 Exudate Management

Table 1 Evaluate changes in exudate status¹²

	Indicators		
Status	Wound bed	Dressing	Surrounding skin
Dry	Wound bed is dry; there is no visible moisture	Primary dressing is unmarked; dressing may be adherent to wound	Skin may be scaly, atrophic, hyperkeratotic
Moist	Small amounts of fluid are visible when dressing is removed; wound bed may appear glossy	Primary dressing may be lightly marked; dressing change frequency is appropriate	Skin is likely to be intact, hydrated, no lesions
Wet	Small amounts of fluid are visible when the dressing is removed	Primary dressing is extensively marked, but strikethrough does not	Initial fragmented areas of maceration may be apparent

Title: CIP with integrated central Amendments 1 and 2 ExufiberAg+01
Page 36(50)

Investigation Code	ExufiberAg+01Final Version	Approval date	2017-05-10
		Amendment 1 Approval date	2017-05-26
		Amendment 2 Approval date	2018-08-07
		Amendment 3 Approval date	2018-08-21
		Amendment 4 Approval date	2019-02-19

		occur; appropriate dressing change frequency	
Saturated	Free fluid is visible when the dressing is removed	Primary dressing is wet and strikethrough occurs; dressing change is required more frequently than usual	Peri-wound skin is likely to be macerated or denuded with extensive involvement
Leaking	Free fluid is visible when the dressing is removed	Dressings are saturated and exudate is escaping from primary and secondary dressings onto clothes or beyond; dressing change is required much more frequently than usual	Peri wound skin is likely to be macerated or denuded with extensive involvement

4.5.7 Signs of local infection split between acute and chronic wound

Figure 3 Local infection, definition for acute and chronic wounds⁸

Signs and symptoms of localised infection in wounds.
ACUTE WOUNDS e.g. surgical or traumatic wounds, burns

 Classical signs and symptoms: 
 new or increasing pain erythema local warmth swelling purulent discharge Pyrexia Delayed or stalled healing Abscess Malodour
CHRONIC WOUNDS e.g. diabetic foot ulcers, venous leg ulcers, arterial leg/foot ulcers, pressure ulcers

 New, increased or altered pain Delayed (or stalled) healing Periwound oedema Bleeding or friable (easily damaged) granulation tissue Distinctive malodour or change in odour Wound bed discolouration Increased, altered or purulent exudate

Title: CIP with integrated central Amendments 1 and 2 ExufiberAg+01

Page 37(50)

Investigation Code	ExufiberAg+01Final Version	Approval date	2017-05-10
		Amendment 1 Approval date	2017-05-26
		Amendment 2 Approval date	2018-08-07
		Amendment 3 Approval date	2018-08-21
		Amendment 4 Approval date	2019-02-19

- Induration (hardening of a tissue, particularly the skin, caused by inflammation)
- Pocketing-granulation tissue does not grow in a uniform manner across the entire wound, pockets can harbour bacteria
- Bridging-presence of strands of tissue across the wound bed

Title: CIP with integrated central Amendments 1 and 2 ExufiberAg+01

Page 38(50)

Investigation Code	ExufiberAg+01Final Version	Approval date	2017-05-10
		Amendment 1 Approval date	2017-05-26
		Amendment 2 Approval date	2018-08-07
		Amendment 3 Approval date	2018-08-21
		Amendment 4 Approval date	2019-02-19

4.5.8 Anticipated ADEs

The following possible clinical outcomes have been identified as anticipated adverse device effects in connection to the risks evaluated in the Product Risk Management Record for:

Exufiber Ag+

- Maceration
- Prolonged wound healing
- Leakage leading to cross contamination or infection
- Infection due to contamination
- Bacterial growth/Infection
- Discolouration
- Local allergic reaction
- Sensitisation, cytotox, skin irritation
- Selection for resistant microorganisms
- Anaemia due to potential systemic absorption of silver

Exufiber

- Maceration
- Prolonged wound healing
- Dressing related pain and/or trauma to the wound bed and edges
- Infection

Aquacel Ag Extra is assumed to have the same identified risk as Exufiber Ag+, since Exufiber Ag+ is substantially equivalent with Aquacel Ag Extra.

The investigator should take the above mentioned list of events in consideration when reporting and assessing events in accordance with section 9 of the CIP.

Based on the risk management record it can be concluded, that for Exufiber Ag+, Exufiber and Aquacel Ag Extra, there are no unacceptable risks of harm for the patient, the user nor third part involved in this clinical investigation, if the treatment dressings are used under normal conditions and within its intended use.

Before reaching the above conclusion, the identified risks of the investigational device, which had been ranked for severity, occurrence and detectability according to Mölnlycke risk management process, were mitigated as far as possible in the risk management process (following ISO 14971, Application of Risk Management to Medical Devices).

4.6 Data Quality Assurance

4.6.1 Monitoring, Audits and Inspections

During the investigation, the monitor will have regular contacts with the investigation site. These contacts will include visits to confirm that the facilities remain adequate to specified standards

Title: CIP with integrated central Amendments 1 and 2 ExufiberAg+01

Page 39(50)

Investigation Code	ExufiberAg+01Final Version	Approval date	2017-05-10
		Amendment 1 Approval date	2017-05-26
		Amendment 2 Approval date	2018-08-07
		Amendment 3 Approval date	2018-08-21
		Amendment 4 Approval date	2019-02-19

and that the investigation site team is carrying out the procedure stated in the clinical investigation plan and supports the investigator. All data must be accurately recorded in the eCRF. Source data verification (a comparison of data in the eCRF with the subject's hospital/practice and other records at the investigation site) with direct access to records will also be performed.

A Monitoring Plan will be developed to be followed by the monitor.

The monitor, delegate or other Mölnlycke personnel will be available between visits if the investigator or other staff at the site needs information and/or advice.

Authorized representatives of Mölnlycke and/or a Competent Authority (CA) and/or the Institutional

Review Board (IRB) may visit the investigation site to perform audits/inspections, including source data verification.

4.6.2 Training of Staff

The Principal Investigator will ensure that appropriate training relevant to the investigation is given to investigators and investigation site staff as well as community nurses and that new information of relevance to the performance of this investigation is forwarded to the staff involved. The Principal Investigator will also ensure that the involved site staff are experienced in wound care.

Before the first subject is entered into the investigation, Mölnlycke personnel or delegate will conduct a site initiation visit. The purpose of the visit is to provide training to the involved personnel including, but not limited to the following items:

- Clinical investigation plan (CIP) and execution thereof
- Good Clinical Practice (GCP)
- Use of eCRF system (Viedoc)
- Use of investigational devices, and additional dressings used in the investigation. A training record will be provided to all trained staff.
- Tissue and Exudate sampling (**only applicable for site no 01 for subjects recruited before September 2018**)
- Safety Handling
- Maintenance of the Investigator Study File

4.6.3 Data Management

The Data Management process includes all activities related to data handling regarding:

- Set-up of eCRF and database
- Specification of on-line checks
- Data entry / Data editing
- Export of data from Viedoc to SAS

Title: CIP with integrated central Amendments 1 and 2 ExufiberAg+01

Page 40(50)

Investigation Code	ExufiberAg+01Final Version	Approval date	2017-05-10
		Amendment 1 Approval date	2017-05-26
		Amendment 2 Approval date	2018-08-07
		Amendment 3 Approval date	2018-08-21
		Amendment 4 Approval date	2019-02-19

- Creation of post-entry checks and listings
- Reconciliation of Serious Adverse Event (SAE), Serious Adverse Device Effect (SADE), Adverse Device Effect (ADE) and Device Deficiency (DD)
- Clean-file process including execution of post-entry checks and listings
- Post clean-file tasks

Viedoc, a web based eCRF system, will be used to capture data in this investigation. The eCRF system complies with FDA Title 21 CFR part 11 (ER/ES) requirement.

eCRF training will be given to appropriate personnel before/at initiation of the investigation site(s).

Data entry will be done by investigators and other authorized personnel at the site(s). When entering data on-line checks are incorporated in Viedoc for consistency and validation.

Pharma Consulting Group will support with a helpdesk function taking care of system user questions regarding Viedoc.

When data has been entered authorized personnel at Mölnlycke can immediately view the data, send queries if necessary and lock eCRF pages when they have been validated.

Photos will be uploaded in Viedoc and are marked with the subject code. Uploaded photos shall not contain any information that can reveal the identity of the subject. All uploaded photos will be reviewed by personnel at Mölnlycke and stored in the company database. All data entered in Viedoc will be encrypted. The physical database will be stored in Sweden.

Records will be retained for a minimum of 10 years after end of the clinical investigation or last product is manufactured whichever is more stringent. In addition investigation sites shall keep their records longer if in accordance with local requirements.

Programs for post-entry checks and data listings will be created and executed for validation of data.

Completeness will be checked by authorized personnel at Mölnlycke so that there are no unexplainable empty fields in Viedoc. This is done in order to prevent that data have been overlooked by personnel entering the data.

A clean-file meeting will be held prior to database lock. All decisions on the evaluability of the data from each individual subject for the statistical analysis must be made and documented before locking the database.

4.7 Statistical Methods and Determination of Sample Size

4.7.1 Statistical Evaluation

General Methodology

The main focus and analysis will be the analysis of the subjects treated with Exufiber Ag+.

The main analyses will be change in primary and secondary efficacy endpoints from baseline to 4 weeks on the ITT population in this group treated with Exufiber Ag+. If missing values at 4 weeks

Title: CIP with integrated central Amendments 1 and 2 ExufiberAg+01

Page 41(50)

Investigation Code	ExufiberAg+01Final Version	Approval date	2017-05-10
		Amendment 1 Approval date	2017-05-26
		Amendment 2 Approval date	2018-08-07
		Amendment 3 Approval date	2018-08-21
		Amendment 4 Approval date	2019-02-19

last observation carry forward (LOCF) will be applied from 1 week.

A sensitivity analysis will be performed for primary analysis with complete cases.

Complementary analyses will be performed on the PP population and for change from baseline to 3 days, 1 week, 2 weeks and 3 weeks.

Since primary efficacy variable and most of the secondary efficacy variables are ordered categorical or dichotomous variables the Sign test will be used for analysis of change within groups for these types of variables and described with number and percentages of improved, not changed and worsened. For primary efficacy variable and important secondary efficacy variables a complete cross tabulation baseline and 4 weeks will be given.

All significance test will be two-sided and conducted at the 5 % significance level.

Continuous variables will be described with mean, SD, median, minimum and maximum and categorical variables will be given with number and percentages. All measured variables will be described by visit.

The statistical analysis of the groups treated with Exufiber or Aquacel Ag Extra will be analysed separately with the same statistical methods as specified above. The database for Exufiber Ag+ will be declared clean and will be analysed before the other two treatment groups are finalised.

Patient Disposition and Data Sets Analysed

The number of subjects included in each of the ITT, PP and safety populations will be summarized. The number and percentage of subjects enrolled and treated will be presented.

Subjects who completed the study and subjects who withdrew from study prematurely will also be presented with a breakdown of the reasons for withdrawal for the ITT, PP and safety populations.

Protocol Violations/Deviations

Major protocol deviations are those that are considered to have an effect on the primary analysis. A list of potential major protocol deviations will be generated programmatically from the data captured before the clean file meeting. The listings from the clinical investigation will be reviewed and the finalisation of the major protocol deviations will be done at the clean file meeting.

The number of patients with major protocol deviations will be summarized.

Demographics and Baseline Characteristics

All variables measured at baseline will be summarized for the ITT- and PP population using appropriate summary statistics for the three treatment groups.

Medical and Surgical History

Listings of all medications collected for each subject by the investigator will be produced.

Prior and Concomitant Medications

Title: CIP with integrated central Amendments 1 and 2 ExufiberAg+01

Page 42(50)

Investigation Code	ExufiberAg+01Final Version	Approval date	2017-05-10
		Amendment 1 Approval date	2017-05-26
		Amendment 2 Approval date	2018-08-07
		Amendment 3 Approval date	2018-08-21
		Amendment 4 Approval date	2019-02-19

Listings of all medications collected for each subject by the investigator will be produced.

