4.7.3 Determination of Sample Size

In the study PUMA 416, with 100 subjects treated with Mepilex without Ag, the result regarding change in Exudate level from baseline to 4 weeks was 56.5 % improved, 32.9 % unchanged and 10.6 % worsened. Assuming the same proportions in this study 38 subjects are needed to find a significant improvement with the Sign test with 95% power and significance level 0.05. If we expect a dropout rate of around 20% we will include 50 subjects in the Exufiber Ag+ treatment group.

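### New maceration and skin irritation are tested only net of resolved baseline cases, and section 4.7 plans no analysis of new onset on the safety population

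*Combined protocol and SAP*

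**What the plan says.** Section 4.5.8 lists outcomes that "have been identified as anticipated adverse device effects". Maceration is listed for Exufiber Ag+ and for Exufiber. Skin irritation is listed for Exufiber Ag+ only. Aquacel Ag Extra is assumed to share the Exufiber Ag+ risks.

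Section 4.5.2 places the matching ratings among the secondary performance variables: the item "Maceration under the Primary dressing (Y/N"), its counterpart outside the dressing, and redness/irritation under and outside the dressing. The schedule in 4.2.1 has these rated at baseline and at every later visit.

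In 4.7.1, for ordered and dichotomous variables, "the Sign test will be used for analysis of change within groups for these types of variables". The same sentence requires the number and percentage improved, unchanged and worsened. The main comparison is baseline to 4 weeks, with complementary comparisons at earlier time points and a description of every variable by visit. A baseline-by-4-week cross tabulation is promised for the primary variable and for important secondary variables, which are not listed. On testing, "All significance test will be two-sided and conducted at the 5 % significance level".

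Section 2 states a safety objective. Section 4.5.3 lists infection signs and AE/ADE/SAE/SADE/DD as safety variables. Section 4.7 uses the safety population for counts and disposition, but specifies no analysis of any safety outcome on it.

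**The concern.** A subject who already has the sign at baseline can only improve or stay the same. A new case can arise only in a subject who starts without it. Baseline maceration may well be common: entry requires Wet to Leaking wounds, and Table 1 in 4.5.6 says of Saturated and Leaking wounds that "Peri-wound skin is likely to be macerated or denuded with extensive involvement", while at Wet some maceration may already show.

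The Sign test compares those who lost the sign with those who gained it. Its p-value therefore mixes resolution of the presenting condition with onset of a sign that the plan itself anticipates as a device effect. If that p-value is the only inference reported for these signs, a statement that maceration improved can be true of the net change and still say nothing about how often it newly appeared. That second figure is the one a safety objective needs, and it is not planned.

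**Working it through.** **The plan's own figure.** Section 4.7.3 assumes, for exudate, "56.5 % improved, 32.9 % unchanged and 10.6 % worsened" and concludes that "38 subjects are needed to find a significant improvement with the Sign test with 95% power and significance level 0.05".
- Share changing: 0.565 + 0.106 = 0.671. Share improved among those changing: 0.565/0.671 = 0.842.
- With 25 changed subjects the two-sided critical value is 18 and exact power is 0.966. Then 25/0.671 = 37.3, which rounds up to 38.
- Dropout: 38/0.8 = 47.5, which rounds up to 48 and is within the 50 enrolled.

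The figure reproduces and is not in dispute. It concerns exudate, and no corresponding figure is given for maceration or irritation.

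**Inputs for the illustration.** N = 50 is the Exufiber Ag+ enrolment in 4.7.3. The documents give no maceration rate, so the following are assumptions: 60% macerated at baseline, 60% of those resolve, 30% of the rest newly macerate.
- Macerated at baseline: 0.60 × 50 = 30. At risk: 50 − 30 = 20.
- Resolved: 0.60 × 30 = 18. New: 0.30 × 20 = 6.
- Sign test: 2 × P(X ≥ 18), X ~ Binomial(24, 0.5), p = 0.023, in favour of improvement.
- Percentage worsened as planned: 6/50 = 12%.
- New onset among those at risk: 6/20 = 30%, Clopper-Pearson 95% CI 11.9% to 54.3%.

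**The same six new cases under different amounts of resolution:**

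| Resolved | New | Two-sided p | Direction |
|---|---|---|---|
| 0 | 6 | 0.031 | worsening |
| 12 | 6 | 0.24 | neither |
| 18 | 6 | 0.023 | improvement |

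The number of new cases is fixed, and the conclusion turns on how many baseline cases resolved.

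**Other assumed inputs.**
- 35 of 50 macerated at baseline, same rates: 21 resolved, and 0.30 × 15 = 4.5 new. Four new cases give p = 0.0009 and 4/15 = 27% (CI 7.8% to 55.1%). Five give p = 0.0025 and 5/15 = 33%.
- 20 macerated at baseline, all resolving: 8 new cases still give p = 0.036 for improvement, with 8/30 = 27% of those at risk.
- 15 resolved, 5 new: p = 0.041 for improvement. Worsened is 5/50 = 10%. With 15, 20, 25 or 30 macerated at baseline, new onset among those at risk is 5/35 = 14%, 5/30 = 17%, 5/25 = 20% or 5/20 = 25%.

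**Accumulation over visits.** With 20 at risk, suppose 6 have new maceration at Visit 2 and 6 have it at Visit 5. If they are the same subjects, 6/20 = 30% were ever affected. If they are all different, 12/20 = 60% were. Separate tables by visit look the same in both cases.

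**The case against.** The strongest reply is that the plan does not rest on the p-value alone. The sentence that prescribes the Sign test also requires the number worsened, which for a yes/no sign is the number of new cases. Section 4.7.1 adds comparisons at earlier time points and a description by visit, so a case present at Visit 2 or 3 and gone by 4 weeks still appears. It also summarises all baseline variables, so the number free of the sign at baseline is reported and, missing data aside, the 4-week at-risk percentage can be worked out by hand. All of this stands. A reader might infer that the plan hides new harm, and the documents do not support that.

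Four further readings are tempting and also fail:
- That stalled healing is treated only as performance. Section 4.5.3 lists delayed or stalled healing as a safety variable for both acute and chronic wounds.
- That wound status is netted in the same way. Its categories are already relative to baseline, so the argument for a yes/no sign does not carry over.
- That nothing connects these ratings to event reporting. Section 4.5.8 tells investigators to bear the list in mind when reporting, AE/ADE are collected at every visit, and 4.6.3 includes ADE reconciliation.
- That every new Yes is an ADE. Section 9 requires a relation to the dressing, with causality judged by the investigator and the sponsor.

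The reply does not supply a count of subjects ever newly affected. The cross tabulation covers only 4 weeks and an unnamed set of variables. ADE reports reflect a causality judgement and are given no tabulation in 4.7. Maceration is absent from the structured safety signs in 4.5.3, and redness appears there only as erythema within an acute-wound composite.

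**Conclusion.** The point holds as a gap in the safety analysis, not as concealment. For two signs that correspond to anticipated effects of Exufiber Ag+, the only inference planned is a net one, and 4.7 has no analysis of a safety outcome on the safety population. New cases at each visit will be visible, but diluted by subjects who cannot worsen and never accumulated per subject.

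On the assumed rates the dilution is 12% against 30%. With 5 new cases and 15 to 30 of 50 macerated at baseline it is 10% against 14% to 25%. These sizes rest wholly on assumed baseline, resolution and onset rates. Maceration is likely only at Saturated and Leaking, and the baseline mix is unknown, so the effect would be smaller if most subjects enter as Wet without maceration. That the Sign test p-value cannot serve as a safety result does not depend on those rates. The primary analysis and the sample size are unaffected.

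**What to change.** Add a safety paragraph to 4.7, on the safety population, before the Exufiber Ag+ database is declared clean:
- For maceration and for redness/irritation, report the number and percentage, with exact 95% CI, of subjects with the sign absent at baseline and present at any later visit. The denominator is those absent at baseline.
- Show this beside a table of reported ADEs, labelled as new-onset signs and not as ADEs.
- Name these variables among those that receive the baseline-by-4-week cross tabulation.
- State that the Sign test p-value for these variables describes net change and is not a safety result.

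The data are already scheduled at every visit. The cost is one extra table and a reported figure that will look less favourable than the percentage worsened.
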